9.2 Causality

Not related or improbable: a clinical event including laboratory test abnormality with temporal relationship to trial treatment/intervention administration that makes a causal relationship incompatible or for which other treatments, chemicals or disease provide a plausible explanation. This will be counted as "unrelated" for notification purposes.

Page 56 of 71 Treat to target in gout Protocol Final Version 1.1 date 29 May 2019

Possible: a clinical event, including laboratory test abnormality, with temporal relationship to trial treatment/intervention administration that makes a causal relationship a reasonable possibility, but which could also be explained by other interventions, chemicals or concurrent disease. This will be counted as "related" for notification purposes.

Probable: a clinical event, including laboratory test abnormality, with temporal relationship to trial treatment/intervention administration that makes a causal relationship a reasonable possibility, and is unlikely to be due to other interventions, chemicals or concurrent disease. This will be counted as "related" for notification purposes.

Definite: a clinical event, including laboratory test abnormality, with temporal relationship to trial treatment/intervention administration that makes a causal relationship a reasonable possibility, and which can definitely not be attributed to other causes. This will be counted as "related" for notification purposes.

With regard to the criteria above, medical and scientific judgment shall be used in deciding whether prompt reporting is appropriate in that situation.

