6.1.3 Safety outcomes

- New intervention-related AEs reported during the study,
- Discontinuation due to intervention-related AEs.

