9.3 Reporting of adverse events

Participants will be asked to contact the study site immediately in the event of any SAE. All adverse events will be recorded and closely monitored until resolution, stabilization, or until it has been shown that the study treatment is not the cause. The Chief Investigator shall be informed immediately by email and a follow-up phone call of any SAE and shall determine seriousness and causality in conjunction with any treating medical practitioners.

In the event of a pregnancy occurring in a trial participant or the partner of a trial participant, the participant will be advised to consult their GP as per usual care to discontinue treatment at the discretion of the GP. The outcome will be recorded on the participants CRF.

All treatment-related serious adverse events will be recorded and reported to the Research Ethics Committee (REC) as part of the annual reports. Unexpected intervention related SAE will be reported within the timeframes to the REC as stated below. The Chief Investigator shall be responsible for all adverse event reporting. ER, a clinically active co-investigator with interest in gout research and co-CI on the NIHR grant, will deputise for the Chief Investigator when he is away. If both are away then MS and CMD, both academic GPs, will deputise for the Chief Investigator.

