9.4 Trial Treatment / Intervention Related SAEs

A serious adverse event that is unexpected in its severity and seriousness *and* deemed directly related to or suspected to be related to the trial treatment or intervention shall be reported to the ethics committee that gave a favourable opinion as stated below. The event shall be reported immediately of knowledge of its occurrence to the Chief Investigator.

The Chief Investigator will:

• Assess the event for seriousness, expectedness and relatedness to the trial treatment or intervention.

Page 57 of 71 Treat to target in gout Protocol Final Version 1.1 date 29 May 2019

- Take appropriate medical action, which may include halting the trial, and inform the Sponsor of such action.
- If the event is deemed related to the trial treatment or intervention, inform the REC using the reporting form found on the HRA web page within 7 days of knowledge of the event.
- Within a further eight days send any follow-up information and reports to the REC.
- Make any amendments as required to the study protocol and inform the REC as required

Expected SAEs such as hospitalization due to gout flare, side-effects of ULT or flare prophylaxis e.g. diarrhoea due to colchicine will not be reported to the ethics committee.

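### The causality categories in section 9.2 overlap: a serious adverse event with plausible timing and a plausible alternative cause fits both an unrelated and a related category, and no rule says which prevails

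*Protocol*

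**What the plan says.** Protocol section 9.2 sets four causality categories and attaches a counting rule for notification to each.

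- *Not related or improbable* has two limbs. The first is an event "with temporal relationship to trial treatment/intervention administration that makes a causal relationship incompatible". The second follows at once: "or for which other treatments, chemicals or disease provide a plausible explanation". Events in this category count as unrelated.
- *Possible* is an event with a temporal relationship "that makes a causal relationship a reasonable possibility, but which could also be explained by other interventions, chemicals or concurrent disease". It counts as related.
- *Probable* and *Definite* also require timing that makes causation a reasonable possibility, with other causes unlikely or excluded. Both count as related.

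The label is then used in these places:

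- Section 9.1 has every adverse event assessed for causality.
- Under section 9.3 the chief investigator "shall determine seriousness and causality in conjunction with any treating medical practitioners", and treatment-related SAEs go into the annual REC reports.
- Section 9.4 deals with unexpected SAEs that are related or suspected to be related: "If the event is deemed related to the trial treatment or intervention, inform the REC", within 7 days. It exempts expected SAEs from reporting to the ethics committee.
- Section 6.1.3 lists two safety outcomes, "New intervention-related AEs reported during the study" and discontinuation because of such events.

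**The concern.** The second limb of *Not related or improbable* carries no timing condition. A plausible alternative explanation is enough by itself to make an event unrelated. The presence of another possible explanation is also what distinguishes *Possible* from the two higher categories, and *Possible* counts as related. One feature of an event thus leads to opposite counts, depending on which definition is applied.

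Such events are not exotic. Section 6.7.2 excludes only eGFR below 30 ml/min, so people with moderately reduced renal function can enter. An admission with worsening renal function in such a participant could have plausible timing and a plausible cause in the pre-existing disease.

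At stake are consistent coding of relatedness and the REC reporting that depends on it. The GP and usual care team know the allocation (section 6.4.2), and treating practitioners take part in the causality decision (section 9.3). A rule that permits either code therefore leaves room for unintended bias.

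**Working it through.** No figure in the protocol bears on this point, so the check is logical.

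**Notation, taken from section 9.2**

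- T: the timing makes causation a reasonable possibility.
- I: the timing makes causation incompatible.
- A: another treatment, chemical or disease plausibly explains the event.

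**The categories as written**

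| Category | Condition | Counted for notification |
|---|---|---|
| Not related or improbable | I or A | unrelated |
| Possible | T and A | related |
| Probable | T, other causes unlikely | related |
| Definite | T, other causes excluded | related |

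**Overlap.** The conditions (I or A) and (T and A) are both met whenever T and A hold. Every event that meets *Possible* through a plausible alternative explanation therefore also meets the second limb of *Not related or improbable*. The two higher categories do not overlap in this way, because they require other causes to be unlikely or excluded.

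**Is there a tie-break?** Three places might supply one.

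1. The closing sentence of section 9.2 leaves to judgment whether prompt reporting is appropriate. It does not say which category applies.
2. Section 9.4 covers events that are related or suspected to be related. This favours reporting a T-and-A event, but the REC step starts once the event is deemed related, and section 9.2 allows the same event to be counted unrelated.
3. Section 9.3 follows events until the study treatment has been shown not to be the cause. That is a stricter standard than a plausible alternative, but it governs follow-up and not classification.

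None of these settles the category.

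**What follows for a T-and-A event**

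| Item | Coded unrelated | Coded related |
|---|---|---|
| Annual REC report of treatment-related SAEs (9.3) | not included | included |
| 7-day REC report, unexpected SAE (9.4) | not triggered | triggered |
| Immediate notice of an SAE to the chief investigator (9.3) | yes | yes |
| Adverse event and SAE totals (8.8, Table 13) | counted | counted |
| Intervention-related outcomes (6.1.3) | probably not counted | probably counted |

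The last row says probably because section 9.2 ties its counts to notification and section 6.1.3 does not cite it. The link is an inference from the fact that section 9.2 contains the only causality scale in the document.

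**The case against.** The strongest reply is that the definitions should be read with their labels. An event cannot sensibly be both improbable and a reasonable possibility. The verbs differ too: in the first category another cause provides a plausible explanation, while under *Possible* it merely could explain the event. If any plausible alternative made an event unrelated, *Possible* would be almost empty, and a reading that empties a defined category is unlikely to be the intended one. This shows what the authors probably meant. It does not change the unconditional "or" limb that an assessor will apply, and the difference between the verbs is too fine to separate the categories reliably.

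The safeguards also stand. Every SAE goes to the chief investigator at once, causality is decided by the chief investigator or a named deputy, the DMC reviews unblinded safety data, and section 9.4 leans towards reporting. They narrow the consequences without supplying the missing rule.

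Some stronger readings are tempting, but the protocol does not support them.

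- A reader might infer that the closing judgment sentence of section 9.2 contradicts the immediate notification in sections 9.3 and 9.4. It does not cancel notice of an SAE to the chief investigator.
- A reader might take the interacting drugs in Appendix 1, or several study drugs given together, as common alternative causes. Appendix 1 lists drugs that raise colchicine concentration, which makes a study drug a more likely contributor. Prophylaxis is part of the intervention (section 7.1), so an event caused by it is still intervention-related. Comorbidity is the sound example.

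**Conclusion.** The overlap is real on the plain wording of section 9.2, and nothing in the protocol resolves it. It reaches REC reporting of SAEs directly: annually for treatment-related ones, and within 7 days for unexpected related ones. It probably also reaches the two outcomes in section 6.1.3, on the assumption that the only causality scale in the document is the one used for them.

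Total adverse event and SAE counts, the primary analysis and the sample size are unaffected. It would go too far to say that the split formally defines the safety outcomes, or that section 9.4 clearly permits an expedited report to be withheld.

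The size of the effect cannot be estimated from the protocol. A reader might quantify it as 1/(1 − p), where p is the share of events with plausible timing that also have a plausible alternative cause. That gives 1/0.7 = 1.4 at p = 30% and 1/0.3 = 3.3 at p = 70%. The protocol gives no value for p, and the formula compares two extremes in which all such events are coded one way or all the other. It is not a forecast. The point merits correction because one stated rule gives opposite results for the same event and the change is small.

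**What to change.** Make the categories in section 9.2 mutually exclusive.

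1. Limit *Not related or improbable* to events for which causation is not a reasonable possibility. Joining the two limbs with "and" would also remove the overlap, but by itself it would leave an event with incompatible timing and no alternative explanation in no category, so the general wording is safer.
2. State that an event whose timing makes causation a reasonable possibility is at least *Possible* and is counted as related, even if another explanation exists. This agrees with the suspected-relatedness wording in section 9.4.
3. In section 6.1.3, say whether intervention-related means the related categories of section 9.2.

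The judgment sentence at the end of section 9.2 need not be deleted. The cost is a few sentences in the protocol and matching guidance on the adverse event form, and somewhat more SAEs will be counted as related and reported to the REC.

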9.3 Reporting of adverse events

Participants will be asked to contact the study site immediately in the event of any SAE. All adverse events will be recorded and closely monitored until resolution, stabilization, or until it has been shown that the study treatment is not the cause. The Chief Investigator shall be informed immediately by email and a follow-up phone call of any SAE and shall determine seriousness and causality in conjunction with any treating medical practitioners.

In the event of a pregnancy occurring in a trial participant or the partner of a trial participant, the participant will be advised to consult their GP as per usual care to discontinue treatment at the discretion of the GP. The outcome will be recorded on the participants CRF.

All treatment-related serious adverse events will be recorded and reported to the Research Ethics Committee (REC) as part of the annual reports. Unexpected intervention related SAE will be reported within the timeframes to the REC as stated below. The Chief Investigator shall be responsible for all adverse event reporting. ER, a clinically active co-investigator with interest in gout research and co-CI on the NIHR grant, will deputise for the Chief Investigator when he is away. If both are away then MS and CMD, both academic GPs, will deputise for the Chief Investigator.

9.4 Trial Treatment / Intervention Related SAEs

A serious adverse event that is unexpected in its severity and seriousness *and* deemed directly related to or suspected to be related to the trial treatment or intervention shall be reported to the ethics committee that gave a favourable opinion as stated below. The event shall be reported immediately of knowledge of its occurrence to the Chief Investigator.

The Chief Investigator will:

• Assess the event for seriousness, expectedness and relatedness to the trial treatment or intervention.

Page 57 of 71 Treat to target in gout Protocol Final Version 1.1 date 29 May 2019

- Take appropriate medical action, which may include halting the trial, and inform the Sponsor of such action.
- If the event is deemed related to the trial treatment or intervention, inform the REC using the reporting form found on the HRA web page within 7 days of knowledge of the event.
- Within a further eight days send any follow-up information and reports to the REC.
- Make any amendments as required to the study protocol and inform the REC as required

Expected SAEs such as hospitalization due to gout flare, side-effects of ULT or flare prophylaxis e.g. diarrhoea due to colchicine will not be reported to the ethics committee.

9.5 Participant removal from the study due to adverse events

Any participant who experiences an adverse event may be withdrawn from the study at the discretion of the Investigator.

10. ETHICAL AND REGULATORY ASPECTS

10.1 ETHICS COMMITTEE AND REGULATORY APPROVALS

The trial will not be initiated before the protocol, informed consent forms and participant and GP information sheets have received approval or favourable opinion from the REC, the respective NHS or other healthcare providers Research & Development (R&D) department, and the Health Research Authority (HRA) if required. Should a protocol amendment be made that requires REC approval, the changes in the protocol will not be instituted until the amendment and revised informed consent forms and participant and GP information sheets (if appropriate) have been reviewed and received approval or favourable opinion from the REC and R&D departments. A protocol amendment intended to eliminate an apparent immediate hazard to participants may be implemented immediately providing that the REC are notified as soon as possible and an approval is requested. Minor protocol amendments only for logistical or administrative changes may be implemented immediately, and the REC will be informed.

The trial will be conducted in accordance with the ethical principles that have their origin in the Declaration of Helsinki, 1996; the principles of Good Clinical Practice, and the UK Department of Health Policy Framework for Health and Social Care, 2017.

10.2 INFORMED CONSENT AND PARTICIPANT INFORMATION

The process for obtaining participant informed consent will be in accordance with the REC guidance, and Good Clinical Practice (GCP) and any other regulatory requirements that might be introduced. The investigator or their nominee and the participant shall both sign and date the Informed Consent Form before the person can participate in the study.

The decision regarding participation in the study is entirely voluntary. The investigator or their nominee shall emphasize to potential participants that consent regarding study participation may be withdrawn at any time without penalty or affecting the quality or quantity of their future medical care, or loss of benefits to which the participant is otherwise entitled. No trial-specific interventions will be performed before informed consent has been obtained.

Page 58 of 71 Treat to target in gout Protocol Final Version 1.1 date 29 May 2019

The investigator will inform the participant of any relevant information that becomes available during the course of the study, and will discuss with them whether they wish to continue with the study. If applicable they will be asked to sign revised consent forms.

If the Informed Consent Form is amended during the study, the investigator shall follow all applicable regulatory requirements pertaining to its approval by the REC and use of the amended form (including for ongoing participants).

10.3 RECORDS

10.3.1 Case Report Forms (CRF)

Each person is allocated a unique study number on mailing of the eligibility questionnaire, so that only anonymised data are used for analysis. The unique study numbers will be generated from the study database and provided to each practice for use when mailing. The number will be made up of site ID followed by a sequence of unique numbers. The study number will be for use on CRFs other trial documents and the electronic database. The documents will also use their initials (of first and last names separated by a hyphen) and date of birth (dd/mm/yy).

CRFs will be treated as confidential documents and held securely in accordance with regulations. The investigator at site will make a separate confidential record of the participant's name, date of birth, local hospital number or NHS number, and Participant Trial Number (the Trial screening Log), to permit identification of all participants enrolled in the trial, in accordance with regulatory requirements and for follow-up as required which will be securely stored and remain at the investigator site. CRFs shall be restricted to those personnel approved by the Chief or local Principal Investigator and recorded on the 'Trial Delegation Log.'

All paper forms shall be filled in using black ballpoint pen. Errors shall be lined out, but not obliterated by using correction fluid, and the correction inserted, initialled and dated.

The Chief or local Principal Investigator shall sign a declaration ensuring accuracy of data recorded in the CRF.

Personal data will be available to investigators working in the GP surgeries. A copy of each participant paper CRF will be sent securely to Keele CTU but will not be sent with any patient identifiable information. Electronic data for the study will be stored securely within a Microsoft SQL Server database, hosted in a secure infrastructure at Keele CTU. Access to patient identifiable data is highly restricted using pre-defined roles and privileges, and restricted views of the data so that authorised study team members see only the data that is required to carry out their role. Data access is fully auditable within this system.

10.3.2 Sample labelling

Samples for NHS pathology analysis will be labelled in accordance with local NHS procedures.

10.3.3 Source documents

Source documents shall be filed at the investigator's site (GP surgery) and a copy will be held at Keele Clinical Trials Unit up until the point at which documents are transferred to the sponsor for archiving. A CRF may also completely serve as its own source data. Only trial staff as listed

Page 59 of 71 Treat to target in gout Protocol Final Version 1.1 date 29 May 2019

on the Delegation Log shall have access to trial documentation other than the regulatory requirements listed below.

10.3.4 Direct access to source data/documents

The CRF and all source documents, including progress notes and copies of laboratory and medical test results as applicable shall be made available at all times for review by the Chief Investigator, Sponsor's designee and inspection by relevant regulatory authorities (e.g. DH, Human Tissue Authority).

10.4 DATA PROTECTION

All trial staff and investigators will endeavour to protect the rights of the trial's participants to privacy and informed consent, and will adhere to the Data Protection Act, 2018. The CRF will only collect the minimum required information for the purposes of the trial. CRFs will be held securely, in a locked room, or locked cupboard or cabinet. Access to the information will be limited to the trial staff and investigators and relevant regulatory authorities (see above). Confidentiality and anonymity will be maintained for all participants. Any identifying information provided (e.g. names and addresses) will be held in the strictest confidence and stored in a confidential, password protected database accessible by only those with permission. All data used for analysis will be kept separate from participant personal data. Electronic data for the study will be stored securely within a Microsoft SQL Server database, hosted in a secure infrastructure at Keele CTU. Access to patient identifiable data is highly restricted using predefined roles and privileges, and restricted views of the data so that authorised study team members see only the data that is required to carry out their role. Data access is fully auditable within this system.

Information about the trial in the participant's medical records and hospital notes will be treated confidentially in the same way as all other confidential medical information.

11. QUALITY ASSURANCE & AUDIT

11.1 INSURANCE AND INDEMNITY

Insurance and indemnity for trial participants and trial staff will be provided by professional and practice indemnity insurance held by the GP practices. There are no special compensation arrangements, but trial participants may have recourse through the NHS complaints procedures.

The University of Nottingham as research Sponsor indemnifies its staff, research participants and research protocols with both public liability insurance and clinical trials insurance.

